Principal Investigator Site:

Signature and Date:

SUMMARY

TITLE	Stopping Perioperative Angiotensin II Converting					
	Enzyme inhibitors and/or angiotensin-II receptor blockers					
	in major non-cardiac surgery (SPACE): a phase II,					
	explanatory, randomised controlled trial.					
SHORT TITLE	SPACE					
Protocol Version & Date	Version 8.0 28/01/2022					
Methodology	Randomised controlled interventional trial.					
Study Duration	65 months					
Study Centres	Barts Health NHS Trust, University College London					
	Hospitals NHS Foundation Trust, County Durham &					
	Darlington NHS Foundation Trust, Plymouth Hospitals					
	NHS Trust, University Hospitals Bristol NHS Foundation					
	Trust					
Objectives	To determine whether continuing angiotensin-II					
	converting-enzyme inhibitors (ACE-I) and/or angiotens					
	II receptor blockers (ARB) reduces the risk of myocardi					
	injury, identified using high-sensitivity plasma troponin					
	measurement during the first 48 hours after surgery.					
Phase of the Trial	Phase II					
Number of Patients	260 patients (130 per arm)					
Main Inclusion Criteria	Patients aged 60 years and over receiving chronic					
man moraoion ornoria	angiotensin II converting enzyme inhibitors and/or					
	receptor blockers and undergoing major surgery					
	requiring general and/or regional anaesthesia with					
Otationia di Aveloria	sedation.					
Statistical Analysis	The analysis will be conducted on an intention-to-treat					
	basis; all participants with a recorded outcome will be					
	analysed according to the treatment group to which they					
	were randomised.					

GLOSSARY OF TERMS AND ABBREVIATIONS

ACE-I Angiotensin-Converting-Enzyme Inhibitor

ΑE Adverse Event

AR Adverse Reaction

ARB Angiotensin-II Receptor Blocker

BP **Blood Pressure** Chief Investigator CI CRF

Case Report Form

CT Computed Tomography CTA Clinical Trial Authorisation

Clinical Trial of Investigational Medicinal Product **CTIMP**

DSUR Development Safety Update Report

ECG Electrocardiograms

EudraCT European Union Drug Regulating Authorities Clinical Trials

GCP Good Clinical Practice ICF Informed Consent Form

IMP Investigational Medicinal Product

ISF Investigator Site File

JRMO Joint Research Management Office

MHRA Medicines and Healthcare products Regulatory Agency

MΙ Myocardial Infarction

Participant An individual who takes part in a clinical trial

Ы Principal Investigator

PIS **Patient Information Sheet**

1 INTRODUCTION

1.1 Background

A triad of myocardial injury,¹ immunosuppression²,³ and persistent autonomic dysfunction⁴,⁵ is observed in high-risk patients following major surgery, leading to infection, organ failure, delayed recovery and/or death. Prolonged activation of neurohormones such as angiotensin-II correlates with tissue injury.⁶,⁻ Around 40% of surgical patients most at risk of postoperative complications are prescribed angiotensin-II converting enzyme inhibitors (ACE-I) or angiotensin-II receptor blockers (ARB).⁶ These drugs are first-line therapy for improving outcomes from several chronic diseases, including hypertension, chronic kidney disease and cardiac failure. The use of ACE-I and/or ARB is set to rise dramatically, with the recent publication of the landmark SPRINT trial, which shows that lowering blood pressure (BP) control targets to systolic ≤120mmHg reduces mortality.⁶ ACE-I and/or ARB are frequently stopped before surgery in the widely held belief that this prevents intraoperative hypotension, although robust evidence for this is lacking.

1.2 Investigational medicinal product

ACE-I and/or ARB are orally administered drugs prescribed for hypertension, chronic kidney disease and cardiac failure. The choices of ACE-I and/or ARB drugs is already established by the responsible clinician and are not described within this protocol. The responsible clinician can use any other antihypertensive medication for optimal patient care in addition to the ACE-I and/or ARB to achieve target BP in those cases, which remain difficult to control, and if the clinician decides it is required. All investigational medicinal products (IMP) used in this study will be within its' UK licenced indication.

1.3 Preclinical data

ACE-I and/or ARB are established treatments for patients with hypertension, chronic kidney disease and cardiac failure. Drug metabolism, pharmacokinetics and toxicological data are well established for these indications; in the SPACE trial, these drugs will be continued or stopped as per normal clinical practice. The decision to restart ACE-I and/or ARB in SPACE will be confirmed by the Principal Investigator (PI) at each site. There may be a delay in restarting the drugs (for patients in whom they have been stopped preoperatively) on postoperative day 2, if BP is low and/or the presence of acute kidney injury, according to the protocol criteria.

1.4 Clinical data

UK practice and international guidelines reflect clinical uncertainty regarding ACE-I and/or ARB withdrawal.^{1,2} However, a strong association exists between stopping ACE-I and/or ARB and an increased risk of mortality.^{3,4} These epidemiologic data suggest that acute withdrawal of ACE-I and/or ARB, coupled with upregulation of the angiotensin receptor as a result of chronic ACE-I and/or ARB therapy and substantial elevations in angiotensin-2, could be directly injurious, leading to excess postoperative morbidity and mortality. This hypothesis is highly plausible since the use of ACE-I and/or ARB reduces cardiovascular morbidity,^{5,6} and inflammation,⁷ particularly in patients with established cardiovascular and chronic kidney disease.

1.5 Rationale and risks/ benefits

We do not currently know whether ACE-I and/or ARB should be stopped or continued in major surgery. Furthermore, our current mechanistic understanding suggests that ACE-I and/or ARB may confer organ protection in the perioperative period. There may be benefits of administering these drugs throughout the perioperative period, by counteracting the harmful effects of high levels of angiotensin-II following the stress of surgery. There may also be harm as a result of lowering BP, which can affect kidney function and the heart. There is an acceptable risk-benefit ratio, exemplified by the fact that some clinicians continue these drugs while others stop them prior to surgery in the absence of interventional trial data.

2 TRIAL OBJECTIVES AND DESIGN

2.1 Trial objectives

Primary objective – To determine whether continuing perioperative ACE-I and/or ARB reduces the risk of myocardial injury, identified using high-sensitivity plasma troponin measurement during the first 48 hours after surgery.

Secondary objective – To determine whether continuing perioperative ACE-I and/or ARB reduces the risk of postoperative morbidity.

Tertiary objective – To determine whether continuing perioperative ACE-I and/or ARB results in changes to perioperative heart rate, blood pressure or immune function.

Primary outcome measure

The primary outcome is myocardial injury, a binary variable based on plasma high sensitivity Troponin-T) measured in blood samples collected immediately before the induction of anaesthesia, and then postoperative day 1 ± 6 hours and day 2 ± 6 hours after surgery. The primary outcome is met under the following conditions:

- Troponin-T ≥15 ng/L within 48 hours after surgery with a pre-operative value <15 ng/L

 OR
- Troponin-T increase ≥5 ng/L within 48 hours after surgery with a pre-operative value ≥15ng/L

Secondary outcome measures

- 1. Highest level of Troponin-T measured within 48 hours of surgery (continuous variable)
- 2. Infection within 30 days of surgery*
- 3. Myocardial infarction within 30 days of surgery*
- 4. Acute heart failure within 30 days of surgery*
- 5. Stroke within 30 days of surgery*

Tertiary outcome measures

Changes in heart rate, blood pressure and tests of immune function.

2.2 Safety outcomes

- 1. Hypotension from randomisation until 48 hours after surgery*
- 2. Hypertension from randomisation until 48 hours after surgery*
- 3. Arrhythmias from randomisation until 48 hours after surgery*
- 4. Acute Kidney Injury (KDIGO grades 1-3 within 30 days after surgery*

2.3 Process measures

- 1. Duration of hospital stay after surgery
- 2. Unplanned critical care admission (level 2 and 3), including a planned critical care unit stay prolonged by a complication.

SPACE Protocol v8.0 28.01.2022 Page **11** of **42**

^{*}defined according to clinical criteria, see appendix 2

2.5 Trial design

Phase II, explanatory randomised trial, with open study group allocation and blinded primary outcome assessment.

2.6 Study scheme diagram

3 SUBJECT SELECTION

3.1 Number of subjects and subject selection

Target accrual for the study is 260 patients over 65 months. Patients aged 60 years and over, on chronic ACE-I and/or ARB therapy and undergoing major surgery (e.g. joint replacement, vascular, gastrointestinal surgery) lasting more than 120 minutes requiring general and/or regional anaesthesia with sedation. Patients will be selected for the study from preoperative assessment outpatient clinics and/or referring surgeons (no use of advertisements). Patients will be contacted during their preoperative hospital visit; vulnerable groups will not be included.

SPACE Protocol v8.0 28.01.2022 Page **13** of **42**

3.2 Inclusion criteria

- Informed consent (no incapacitated or vulnerable adult or minors will be included).
- Age 60 years and over.
- Undergoing major surgery (e.g. major joint replacement or vascular or gastrointestinal) requiring general and/or regional anaesthesia with sedation.
- Currently taking ACE-I, ARB or combined ACE-I and ARB therapy or combination therapy where medication includes ACE-I or ARB (e.g. thiazide diuretic and ACE-I).
- Expected duration of surgery longer than 120 minutes.
- American Society of Anesthesiologists physical status grade 3 or above.
- All female subjects must be postmenopausal, as demonstrated by clinical history, or demonstrated not to be pregnant though a preoperative pregnancy test.

3.3 Exclusion criteria

- Current participation in any other trials where care or treatment is being altered.
- Recent myocardial infarction (within 3 months).
- Any condition, which in the opinion of the treating clinician, would result in the patient being harmed by the cessation of the ACE-I and/or ARB therapy.

3.4 Criteria for premature withdrawal

Systematic non-compliance (i.e. not stopping ACE-I and/or ARB on randomisation to that arm, or failure to restart the drug) may result in withdrawal from the study. Once withdrawn no further data will be collected.

4 INVESTIGATIONAL MEDICINAL PRODUCT

4.1 List and definition of each IMP, including placebos

Any ACE-I and ARB licensed for use in the treatment of hypertension, heart failure, chronic kidney disease and/or diabetes mellitus within the UK. Patients will be taking their usual prescribed ACE-I and/or ARB therapy.

SPACE Protocol v8.0 28.01.2022 Page **14** of **42**

As detailed in the British National Formulary, the following ACE-I and ARB medications are currently available and will be discontinued in those participants randomised to the cessation arm of the SPACE trial.

Candesartan	Perindopril Erbumine
Lisinopril	Perindopril Arginine
Irbesartan	Quinapril
Enalapril Maleate	Trandolapril
Telmisartan	Imidapril Hydrochloride
Ramipril	
Eprosartan	
Captopril	
Losartan	
Cilazopril	
Olmesartan	
Fosinopril Sodium	
Valsartan	
Moexipril Hydrochloride	
Azilsartan	

Any new ACE-I or ARB licenced within the study treatment period will also be accepted.

4.2 Formulation of IMP

There will be no IMP to source or label in either arm. Participants are randomised to either continue or stop ACE-I and/or ARB preoperatively. Participating hospital pharmacies will be responsible for the continued supply of medication for participants in each arm throughout the trial as per routine local clinical practice. The medication will be from a commercial stock in standard packaging. As the medication is a continuation of the participant's standard treatment from the local pharmacy's own stock it will not be labelled as an IMP.

4.3 IMP supply

Regulation 46 of The Medicines for Human Use (Clinical Trial) Regulations 2004 allows for a particular situation where specific trial labelling is not required. This applies to trials of marketed products being (a) used within the terms of their marketing authorisation, (b)

SPACE Protocol v8.0 28.01.2022 Page **15** of **42**

dispensed to a subject in accordance with a prescription given by an authorised health care professional and (c) labelled in accordance with the regulations that apply to dispensed relevant medicinal products. IMP in the SPACE trial are marketed products being used within the terms of their marketing authorisation. They will be dispensed to the participant in accordance with a prescription given by an authorised health care professional (the participant's responsible clinician) and will be labelled in accordance with the regulations that apply to dispensed relevant medical products. The medication will be commercial stock in standard packaging. Therefore, specific trial labelling is not required. The IMP to be used in the SPACE trial can be labelled with a standard pharmacy dispensing label under the exemption described above and participants issued with trial information cards. This is clearly documented in the submission in support of the Clinical Trials Authorisation (CTA) application.

4.4 Prescription of IMP

There will be no prescription of IMP by the study team as participants will already be taking the IMP on admission to the study. The study team will only suspend the IMP the participant is usually taking when randomized to withdraw, according to the half-life of the drug, to ensure it has been stopped for an adequate period of time to allow "washout".

4.5 Preparation and administration of IMP

IMP in the SPACE trial are marketed products being used within the terms of their marketing authorisation. The medication will be commercial stock in standard packaging. Specific trial labelling is not required. No changes from local NHS trust standard procedure will occur.

4.6 Prior and concomitant therapies

All prior and concomitant treatments that the subjects take can continue whilst on treatment on the study (this may also include non-medicinal products). The case reporting forms (CRF) will capture data on any prior or concomitant therapies.

4.7 Dose modification/ reduction/ delay

Resumption or continuation of ACE-I and/or ARB in SPACE will not require dose modifications. There may be a delay in restarting the drugs (for patients in whom they have been stopped preoperatively) on postoperative day 2, if BP is low (<90mmHg) and/or the presence of acute kidney injury, according to the protocol criteria (please see study scheme

SPACE Protocol v8.0 28.01.2022 Page **16** of **42**

diagram section 2.6). The decision to restart ACE-I and/or ARB will be confirmed by the PI at each site.

4.8 Return/recall or destruction of IMP

There will be no IMP returns or destructions as part of this study. Drug recall will be through the standard local NHS dispensing pharmacy recall process.

5 STUDY PROCEDURES

5.1 Screening procedures

Potential participants will be screened for eligibility by a member of the research team at the site, having been identified from pre-admission clinic lists, operating theatre lists or surgical wards in the case of patients admitted prior to surgery for other investigations. All patients that undergo screening will be recorded on the screening log. Before surgery, potential participants will be identified and approached by a member of the research team, who are considered part of the direct care team. Due to nature of the intervention patients will not be enrolled on the day of surgery.

5.2 Informed consent procedures

It is the responsibility of the PI or appropriately trained delegate (where possible a medically qualified person) to obtain consent. All staff taking consent will be trained in taking consent and this will be evidenced on the Delegation log, they will also have appropriate Good Clinical Practice (GCP) training. If for some reason an investigator is not available in person or by phone and the participant wishes to speak with them before providing consent, a second consent visit should be arranged. The consent process will include provision of a patient information sheet (PIS) accompanied by an informed consent form (ICF) and, an explanation of the aims, methods, anticipated benefits and potential hazards of the trial. This will either take place face to face or via a locally approved electronic medium (phone, video conferencing etc.). All potential participants will be provided with a copy of the PIS and ICF either in person, via email or by post. If participants agree to take part they would be asked to sign and return the ICF via email or by post. The PI or designee will explain to all potential participants that they are free to refuse to enter the trial or to withdraw at any time during the trial for any reason. Patients who lack capacity to give or withhold informed consent will not be recruited. Patients who are not entered into this trial should be recorded (including reason not entered) on the screening log in the Investigator Site File.

As required by GCP, the patient should be given ample time to consider giving their consent for the trial. It is felt that 24 hours gives sufficient time for the patient to consider their participation within the study and give informed consent. If for any reason, less than 24 hours is to be given, this will be clearly documented in the medical notes along with justification for this decision. The date that the PIS is given to the patient must be documented within the patient's notes to ensure that sufficient time is given (minimum 24 hours).

If any further safety information arises, which may result in significant changes in the risk/benefit analysis, the PIS and ICF must be reviewed and if applicable updated accordingly.

5.3 Randomisation procedures

Once a medically qualified member of the research team has confirmed the patient's eligibility, the process of randomisation can commence. Randomisation will occur after the participant has provided informed consent, but 72 hours before the surgical procedure is due to start. Participants will be centrally allocated to a treatment group in a 1:1 ratio using a computer generated dynamic procedure (minimisation) with a random component.

Minimisation variables are trial centre, surgical procedure category (surgery involving the gut AND all other surgery) and ACE-I/ARB category (ACE-I or ARB). Each participant will be allocated with 80% probability to the treatment group that minimises between group differences in these factors among all participants recruited to the trial to date, and to the alternative group with 20% probability. The allocation sequence is generated by an automated algorithm and is concealed to all trial investigators. The system for generating the allocation sequence is bespoke and was developed in–house; it has been validated for use by the trial statistician, [name], Queen Mary University of London.

To enter a patient into the SPACE trial, research staff at the site will log on to a secure web-based randomisation and data entry platform hosted by Queen Mary University of London and complete the patient's details to obtain a unique patient identification number and treatment group allocation. Patients will receive a patient advice letter confirming their treatment group allocation. In addition, patients will be told in person or by telephone, together with a reminder(s) via text message before hospital admission. Research staff will document randomisation allocation on the CRF. Once the patient has been successfully allocated to a treatment group, this will be documented in the enrolment log.

5.4 Blinding and procedures to minimise bias

This is an open-label trial. Trial participants and staff will not be blinded to treatment group allocation. Local investigators responsible for randomisation and the intervention will not be blinded to treatment group allocation. Where possible, local investigators collecting follow-up data and investigators at the central coordinating centre will be blinded to treatment group allocation. The primary outcome measure (myocardial injury) will be blinded to all investigators until after the last participant has undergone surgery. Since this is an open-label trial, procedures for un-blinding are not required.

5.5 Schedule of treatment for each visit

The trial intervention period will commence 72 hours prior to day of surgery and continue for at least 48 hours after surgery. After randomisation, participants will receive a patient advice letter confirming their treatment group allocation, to stopping or continuing their ACE-I and/or ARB. Participants will also be reminded by telephone call and/or text message, or in person if they are in hospital. If the patients are not in hospital, they will receive a telephone call and/or text message or visit the day before surgery. ACE-I and/or ARB will be continued or discontinued as per treatment group allocation and this will continue until 48 hours after the end of surgery. Since ACE-I and ARB have differing durations of action, participants will receive drug-specific instructions as to when to stop. When the ACE-I and/or ARB duration of action is equal to, or more than, 24 hours, the drug will be stopped 48 hours prior to surgery. All other ACE-I and/or ARB will be stopped on the day before surgery (see appendix for specific drugs' half-life and duration of action).

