5.6 Schedule of assessment in diagrammatic format

Event/Visit	Screening	Pre-op 72 hrs before surgery	Pre-op ≥ 48 hrs before surgery	Day of surgery	Postop day 1 ± 6 hrs	Postop day 2 ± 6 hrs	Postop day 3 ± 6 hrs (if subject was not discharged on postop day 2)	30 days after surgery
Inclusion/exclusion criteria	x							
Informed consent	x							
Demographic information	х							
Medical history	x							
Prior and concomitant medications	x			х	х	х	х	х
Height and weight				Х				
EQ-5D-3L	x							х
Planned level of care	х							
Level of care				Х	Х	Х	х	
Randomisation		Х						
Perioperative information				х				
Review of medical notes	х		х		х	х	х	х
Restart drug						Х		
Blood sample			X*	Х	Х	Х		
Hemoglobin †	x†							
Creatinine †	x†			Х	х	х	x	
Blood pressure/ heart rates				x	x	x		
Intravenous fluids				Х	х	х	х	х
Telephone contact			Х					х
Review of AE/SAE				Х	х	х	х	
End of trial form								х

^{*} provided patient is in hospital.

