18 APPENDICES

Appendix 1: Duration of preoperative cessation required for SPACE trial.

Drug	Time required to stop drug preop (days)
Candesartan	2
Lisinopril	1
Irbesartan	2
Enalapril Maleate	1
Telmisartan	2
Ramipril	1
Eprosartan	2
Captopril	1
Losartan	1
Cilazopril	1
Olmesartan	2
Fosinopril Sodium	1
Valsartan	2
Moexipril Hydrochloride	1
Azilsartan	2
Perindopril	1
Quinapril	1
Trandolapril	5
Imidapril Hydrochloride	1

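### Appendix 1 has trandolapril stopped 5 days before surgery, which fits neither the 72-hour allocation point in 5.3, 5.5 and 5.6 nor either stop time in 5.5

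*Protocol*

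**What the plan says.** Section 5.5 sets the stop time by class. If the duration of action is 24 hours or more, "the drug will be stopped 48 hours prior to surgery. All other ACE-I and/or ARB will be stopped on the day before surgery". Because the second sentence covers every remaining drug, the rule has two outcomes and no third.

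Appendix 1 is the drug-by-drug table of required cessation, in days before surgery. One row reads "Trandolapril 5". Trandolapril is also in the section 4.1 list of drugs that "are currently available and will be discontinued in those participants randomised to the cessation arm of the SPACE trial", so the row is operative.

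Three places fix when the allocation or the intervention begins:

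- Section 5.3: randomisation follows consent, "but 72 hours before the surgical procedure is due to start".
- Section 5.5: "The trial intervention period will commence 72 hours prior to day of surgery".
- Section 5.6: randomisation is marked in the column "Pre-op 72 hrs before surgery".

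Section 4.4 gives the purpose of the stop time. The usual drug is suspended "according to the half-life of the drug, to ensure it has been stopped for an adequate period of time", to allow washout.

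**The concern.** The protocol gives sites two instructions for the same drug and does not say which takes precedence. If Appendix 1 is right, a trandolapril user stopped under 5.5 reaches surgery without the cessation that the protocol itself lists as required, and the contrast between the arms is weakened for that patient. If 5.5 is right, the table has a prescribed drug withheld at least 3 days longer than intended, starting before allocation would normally be known.

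Two sites could each follow the protocol and treat the same patient differently. Adherence also has no single standard for these patients, although section 3.4 allows withdrawal for systematic failure to comply and ends data collection after it. A stop time is a treatment instruction to sites and patients, so it cannot be left to a statistical analysis plan.

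**Working it through.** No sample-size formula applies. The check compares times.

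**Inputs**

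- Appendix 1, trandolapril: 5 days = 5 × 24 = 120 h.
- Section 5.5, longest stop time: 48 h. The other is the day before surgery.
- Sections 5.3 and 5.6, randomisation: 72 h before surgery.
- Section 5.5, start of the intervention period: 72 h before the day of surgery.

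**Step 1: all Appendix 1 rows**

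| Listed interval | Rows | One of the two intervals in 5.5? | Within 72 h? |
|---|---|---|---|
| 1 day (24 h) | 11 | yes | yes |
| 2 days (48 h) | 7 | yes | yes |
| 5 days (120 h) | 1 (trandolapril) | no | no |
| Total | 19 | 18 of 19 | 18 of 19 |

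**Step 2: against the stop rule in 5.5**

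120 − 48 = 72 h. The listed interval is 3 days longer than the longest stop that 5.5 allows.

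**Step 3: against randomisation in 5.3 and 5.6**

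120 − 72 = 48 h. The patient would have to stop 48 h before the allocation exists.

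**Step 4: against the most generous reading of 5.5**

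Count 72 h back from the start of the day of surgery and place the operation as late as possible that day. The time available is less than 72 + 24 = 96 h. 120 − 96 = 24 h, so the shortfall is still more than 24 h.

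**Step 5: what each resolution implies**

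- If Appendix 1 governs, allocation must be at least 120 h before surgery for trandolapril users, and 5.5 needs a third stop time.
- If 5.5 governs, the entry becomes 2 days (duration of action of 24 h or more) or 1 day (otherwise). Either fits within 72 h.

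**The case against.** The strongest reply is that the documents can be read together. Just before the two-level rule, 5.5 promises participants instructions specific to their drug, and the paragraph ends by pointing to the appendix. Section 4.4 ties suspension to half-life. On that view Appendix 1 is the working list, and the sentence in 5.5 is a summary that overlooks one outlier. This is a sensible guess at the intent, but the protocol does not say it. The pointer is to half-life and duration of action, which Appendix 1 does not give. No exception or order of precedence is written, and the rule in 5.5 leaves no room for a third interval.

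A second reply is that 72 hours is meant as a minimum lead time, since patients are recruited from preoperative clinics and randomising at exactly 72 hours is hardly workable. That reading would remove the shortfalls in steps 3 and 4. The text does not state a minimum, however, and the neighbouring column in 5.6 uses a ≥ sign where one is meant. Step 2 stands on either reading.

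Three limits do stand. The advice letter is not part of the protocol, so whether any participant would receive conflicting directions is unknown. The number of trandolapril users is not stated and could be zero. And agreement of the other 18 rows with 5.5 shows only that their values are 1 or 2 days, not that each drug is in its correct class, because durations of action are not listed.

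**Conclusion.** The concern holds. For trandolapril the protocol contradicts itself: 5 days in Appendix 1 against 48 hours or the day before in 5.5, a gap of at least 72 h. With allocation at 72 h, the listed cessation cannot be achieved, by 48 h as written in 5.3 and 5.6 and by more than 24 h on the most generous reading of 5.5. The schedule part of the finding assumes that 72 hours is a fixed time; the conflict with 5.5 does not need that assumption. Both rest on the printed 5 being the intended value, and nothing in the text suggests otherwise.

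The reach is one row of 19, and only cessation-arm users of that drug. The sample size and the intention-to-treat analysis do not change. It should be corrected because it is an operative treatment instruction that cannot be followed consistently as written.

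**What to change.** Choose one of two changes. The clinical team should decide, since the protocol does not give the drug's duration of action.

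- **(a) Keep 5 days.** State in 5.3 and 5.5, with a note to 5.6, that trandolapril users are randomised and told their allocation at least 5 days before surgery, as a named exception to the two-level rule.
- **(b) Let 5.5 govern.** Change the Appendix 1 entry to 2 days if trandolapril's duration of action is 24 hours or more, and to 1 day otherwise.

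In either case, align the patient advice letter with the choice.

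The cost is very low: one table entry, or one added sentence in each of 5.3 and 5.5 with a note to 5.6, plus a matching letter. Under (a), trandolapril users must also be identified early enough to be allocated 5 days ahead. The sample size and analysis stay as they are.
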